8.4.5.3. Occupational Exposure

The investigator must report any instance of occupational exposure to Pfizer Safety within 24 hours of the investigator's awareness using the Vaccine SAE Reporting Form, regardless of whether there is an associated SAE. Since the information about the occupational exposure does not pertain to a participant enrolled in the study, the information is not recorded on a

PFIZER CONFIDENTIAL

CRF; however, a copy of the completed Vaccine SAE Reporting Form must be maintained in the investigator site file.

8.4.6. Cardiovascular and Death Events

Not applicable.

8.4.7. Disease-Related Events and/or Disease-Related Outcomes Not Qualifying as AEs or SAEs

Not applicable.

8.4.8. Adverse Events of Special Interest

Not applicable.

8.4.8.1. Lack of Efficacy

The investigator must report signs, symptoms, and/or clinical sequelae resulting from lack of efficacy. Lack of efficacy or failure of expected pharmacological action is reportable to Pfizer Safety **only if associated with an SAE**.

8.4.9. Medical Device Deficiencies

Medical devices being provided for use in this study are those listed in [Section 6.1.2](#). In order to fulfill regulatory reporting obligations worldwide, the investigator is responsible for the detection and documentation of events meeting the definitions of device deficiency that occur during the study with such devices.

The definition of a medical device deficiency can be found in [Appendix 8](#).

Note: AEs and/or SAEs that are associated with a medical device deficiency will follow the same processes as other AEs or SAEs, as outlined in Sections [8.4.1](#) through [8.4.4](#) and [Appendix 3](#) of the protocol.

8.4.9.1. Time Period for Detecting Medical Device Deficiencies

Medical device deficiencies that result in an incident will be detected, documented, and reported during all periods of the study in which the medical device is used.

Importantly, reportable device deficiencies are not limited to problems with the device itself but also include incorrect or improper use of the device and even intentional misuse, etc.

If the investigator learns of any device deficiency at any time after a participant has been discharged from the study, and such deficiency is considered reasonably related to a medical device provided for the study, the investigator will promptly notify the sponsor.

The method of documenting medical device deficiencies is provided in [Appendix 8](#).

8.4.9.2. Follow-Up of Medical Device Deficiencies

Follow-up applies to all participants, including those who discontinue study intervention.

The investigator is responsible for ensuring that follow-up includes any supplemental investigations as indicated to elucidate the nature and/or causality of the deficiency.

New or updated information will be recorded on a follow-up form with all changes signed and dated by the investigator.

8.4.9.3. Prompt Reporting of Device Deficiencies to the Sponsor

When a device deficiency occurs:

1. The investigator notifies the sponsor by telephone or email within 1 business day of determining that the incident meets the protocol definition of a medical device deficiency.
2. The device deficiency must be recorded on the Medical Device Complaint form.
3. If an AE (either serious or nonserious) associated with the device deficiency occurs, then the AE must be entered into the AE section of the CRF.
4. If an SAE associated with the device deficiency is brought to the attention of the investigator, the investigator must immediately notify Pfizer Safety of the SAE (see [Section 8.4.1.1](#)). All relevant details related to the role of the device in the event must be included in the Vaccine SAE Reporting Form as outlined in Sections [8.4.1.1](#) and [8.4.1.2](#).

The sponsor will be the contact for the receipt of device deficiency information.

8.4.9.4. Regulatory Reporting Requirements for Device Deficiencies

The investigator will promptly report all device deficiencies occurring with any medical device provided for use in the study in order for the sponsor to fulfill the legal responsibility to notify appropriate regulatory authorities and other entities about certain safety information relating to medical devices being used in clinical studies.

The investigator, or responsible person according to local requirements (eg, the head of the medical institution), will comply with the applicable local regulatory requirements relating to the reporting of device deficiencies to the IRB/EC.

8.4.10. Vaccination Errors

Vaccination errors may result from the administration or consumption of the study intervention by the wrong participant, or at the wrong time, or at the wrong dosage strength.

Vaccination errors are recorded and reported as follows:

PFIZER CONFIDENTIAL

Recorded on the Vaccination Error Page of the CRF	Recorded on the Adverse Event Page of the CRF	Reported on the Vaccine SAE Reporting Form to Pfizer Safety Within 24 Hours of Awareness
All (regardless of whether associated with an AE)	Any AE or SAE associated with the vaccination error	Only if associated with an SAE

Vaccination errors include:

- Vaccination errors involving participant exposure to the study intervention;
- Potential vaccination errors or uses outside of what is foreseen in the protocol that do or do not involve the study participant.

Other examples include, but are not limited to:

- The administration of expired study intervention;
- The administration of an incorrect study intervention;
- The administration of an incorrect dosage;
- The administration of study intervention that has undergone temperature excursion from the specified storage range, unless it is determined by the sponsor that the study intervention under question is acceptable for use.

Such vaccination errors occurring to a study participant are to be captured on the medication error page of the CRF, which is a specific version of the AE page.

Whether or not the vaccination error is accompanied by an AE, as determined by the investigator, the medication error is recorded on the medication error page of the CRF and, if applicable, any associated AE(s), serious and nonserious, are recorded on the AE page of the CRF.

In the event of a vaccination dosing error, the sponsor should be notified within 24 hours.

Vaccination errors should be reported to Pfizer Safety within 24 hours on a Vaccine SAE Reporting Form **only when associated with an SAE**.

8.5. Pharmacokinetics

Pharmacokinetic parameters are not evaluated in this study.

8.6. Genetics

8.6.1. Specified Genetics

Specified genetic analyses are not evaluated in this study. [REDACTED]

[REDACTED]

See [Section 10.5](#) for information regarding genetic research. Details on processes for collection and shipment of these samples will be provided separately.

8.6.2. Retained Research Samples for Genetics

Not applicable.

8.7. Biomarkers

Biomarkers are not evaluated in this study.

8.8. Immunogenicity Assessments

Immunogenicity assessments are described in [Section 8.2](#).

8.9. Health Economics

Health economics/medical resource utilization and health economics parameters are not evaluated in this study.

8.10. Study Procedures

Before enrollment and before any study-related procedures are performed, voluntary, written, study-specific informed consent will be obtained from the participant. Each signature on the ICD must be personally dated by the signatory. The investigator or his or her designee will also sign the ICD. A copy of the signed and dated ICD must be given to the participant. The source data must reflect that the informed consent was obtained before participation in the study.

The timing of visit procedures (ie, prior to randomization and after randomization) must be maintained; however, there is flexibility in the order in which the procedures can be conducted at each visit. The ICD must be signed prior to the start of any study procedure.

8.10.1. Visit 1 – Study Intervention Administration – Day 1

Prior to randomization:

- Obtain a personally signed and dated ICD indicating that the participant has been informed of all pertinent aspects of the study before performing any study-specific procedures.
- Assign a participant number via the IRT.

PFIZER CONFIDENTIAL

[REDACTED]

- Obtain and record the participant's demographic information (including date of birth, sex, race, and ethnicity). The complete date of birth (ie, DD-MMM-YYYY) will be collected to critically evaluate the immune response and safety profile by age.
- Perform a clinical assessment. If the clinical assessment indicates that a physical examination is necessary to comprehensively evaluate the participant, perform a physical examination and record any findings in the source documents and, if significant, record such findings on the medical history CRF.
- Measure and record the participant's oral temperature (°F/°C)
- Record nonstudy vaccinations given up to 28 days prior to study intervention administration, in source documents, if applicable (see [Section 6.9](#)).
- If applicable, instruct the participant to use appropriate contraceptives until 28 days after administration of the last dose of study intervention and document the conversation and the participant's affirmation in the participant's source document (see [Section 10.4](#)).
- Perform urine pregnancy test for female participants of childbearing potential (see [Section 8.3.6](#)).
- Ensure and document that all of the inclusion criteria and none of the exclusion criteria are met.
- Assign a randomization number and a study intervention container number via the IRT. This must be the last step before proceeding. A site staff member will prepare the study intervention according to the IPM.

After randomization:

- Collect approximately 60 mL of blood prior to study intervention administration.
- Administer a single 0.25-mL or 0.5-mL injection of the assigned study intervention into the deltoid muscle of the preferably nondominant arm (see [Section 6.1](#)).

PFIZER CONFIDENTIAL

After study intervention administration:

- Site staff will observe the participant for 30 minutes after administration of study intervention for any reactions. Record any acute reactions (including time of onset) in the participant's source documents and on the AE page of the CRF, and on the Vaccine SAE Reporting Form, as applicable. Record concomitant medications used to treat SAEs.
- Record concomitant medications used to treat SAEs, if applicable.
- Record AEs and SAEs as described in [Section 8.4](#).
- Explain the e-diary technologies available for this study ([Section 8.3.1](#)) and assist the participant in downloading the study application onto the participant's own device or issue a provisioned device, if required. Provide instructions on the e-diary's use and completion and ask the participant to complete the e-diary from Day 1 through Day 7, with Day 1 being the day of study intervention administration.
- Issue the participant a measuring device to measure injection site reactions and a digital thermometer and provide instructions on their use.
- Ask the participant to contact the investigator site staff or investigator as soon as possible during the 7-day postadministration period if the participant has redness and/or swelling at the injection site measuring >20 measuring device units (>10 cm) or severe injection site pain (prevents daily activity) to determine if an unscheduled visit is required (refer to [Section 8.10.3](#)).
- Ask the participant to contact the investigator site staff or investigator as soon as possible if he or she experiences a fever $\geq 104^{\circ}\text{F}$ ($\geq 40.0^{\circ}\text{C}$) or any severe systemic event from Day 1 through Day 7 after study intervention administration (where Day 1 is the day of administration) to determine if an unscheduled visit is required (see [Section 8.10.3](#)).
- Ask the participant to contact the site staff or investigator immediately if any significant illness or medical event (eg, emergency room visit or hospitalization) occurs.
- Provide the participant with the participant contact card containing the study and investigator information (see [Section 10.1.11](#)).
- Remind the participant to use appropriate contraceptives until 28 days after study intervention administration, if applicable.
- Schedule an appointment for the participant to return for the next study visit.
- Remind the participant to bring the e-diary to the next visit.
- The investigator or an authorized designee completes the CRF and the source documents and updates the study intervention accountability records.

PFIZER CONFIDENTIAL

- The investigator or appropriately qualified designee reviews the e-diary data online at frequent intervals (daily is optimal) for the 7 days (Day 1 is the day of study intervention administration) following administration to evaluate participant compliance and as part of the ongoing safety review.

8.10.2. Visit 2 – Follow-Up After Study Intervention Administration – 28 to 42 Days After Study Intervention Administration

- Ensure and document that the participant continues to be eligible for the study (see [Section 7](#) for participant discontinuation/withdrawal).
- Record nonstudy vaccinations, if applicable, as described in [Section 6.9](#).
- Discuss contraceptive use since Visit 1 (see [Section 10.4](#)), if applicable, and record any contraceptive use in the source documents.
- Review the participant's e-diary data. Collect stop dates of any e-diary events (local reactions or systemic events) ongoing on the last day that the e-diary was completed and record stop dates in the CRF.
- Collect the participant's e-diary or assist the participant in removing the study application from his or her own personal device.
- Determine if any AEs (including nonserious AEs and SAEs) have occurred since the previous visit, follow up on any previously reported events to determine the outcome (ie, record stop dates or confirm if they are still continuing), record such AEs as described in [Section 8.4](#), and record concomitant medications used to treat SAEs.

- [REDACTED]

- The investigator or an authorized designee completes the CRF and the source documents.

8.10.3. Unscheduled Visit for a Grade 3 Systemic Event or Suspected Grade 4 Reaction

If the participant reports redness or swelling at the injection site measuring >20 measuring device units (>10.0 cm) or severe injection site pain ([Section 8.3.2.1](#)), a temperature >40°C

PFIZER CONFIDENTIAL

[REDACTED]

during the 7 days following study intervention administration at Visit 1, or a severe systemic event ([Section 8.3.2.2](#)) during the 7 days following study intervention administration at Visit 1, a telephone contact must occur as soon as possible between the investigator or medically qualified designee and the participant to assess if an unscheduled investigator site visit is required. A site visit should be scheduled as soon as possible to assess the extent of the injection site reaction unless any of the following is true:

- The participant is unable to attend the unscheduled visit.
- The reaction is no longer present at the time of the telephone contact.
- The participant recorded an incorrect value in the e-diary (confirmation of an e-diary data entry error).
- The PI or authorized designee determined it was not needed.

This telephone contact will be recorded in the participant's source documentation and the CRF. If the participant is unable to attend the unscheduled visit, or the PI or authorized designee determined it was not needed, any ongoing reactions must be assessed at the next study visit. During the unscheduled visit, the reactions should be assessed by the investigator or a medically qualified member of the study staff, such as a study physician or a study nurse, as applicable to the investigator's local practice, who will:

- Measure oral temperature (°F/°C).
- Measure minimum and maximum diameters of redness (if present).
- Measure minimum and maximum diameters of swelling (if present).
- Assess injection site pain (if present) in accordance with the grades provided in [Section 8.3.2.1](#).
- Assess systemic events (if present) in accordance with the grades provided in [Section 8.3.2.2](#).
- Assess for other findings associated with the reaction and record on the AE page of the CRF, if appropriate.

The investigator or an authorized designee will complete the unscheduled visit assessment page of the CRF.

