Local reactions (pain, redness, and swelling) occurring at the injection site and systemic events (fever, fatigue, headache, muscle pain, and joint pain) will be prompted for and collected daily in an e-diary from Day 1 through Day 7 after administration of study intervention, where Day 1 is the day of administration. AEs (including nonserious AEs and SAEs) will be assessed for approximately 1 month after study intervention administration (through Visit 2).

At Visit 2 (28-42 days after Visit 1), participants will return for follow-up. Information will be collected from the participants on AEs and e-diary follow-up (as needed), and blood will be drawn for immunogenicity assessments.

Approximately 15 participants from each group will be enrolled at specialty sites that will collect [REDACTED] and approximately 20 mL for sera for OPA and IgG measurements. The remaining participants enrolled at other sites will have 60 mL of blood drawn for sera for OPA and IgG measurements.

Number of Participants:

Approximately 405 participants (approximately 45 per group) will be randomized to study intervention.

Study Population:

Key inclusion and exclusion criteria are listed below (for the full set of criteria, see [Section 5.1](#) and [Section 5.2](#) of this protocol):

Inclusion Criteria

Participants must meet the following key inclusion criteria to be eligible for enrollment into the study:

1. Male or female participants ≥ 18 and ≤ 49 years of age at the time of consent.
2. Adults determined by clinical assessment (including medical history and clinical judgment) to be eligible for the study, including adults with preexisting stable disease (defined as disease not requiring significant change in therapy or hospitalization for worsening disease) within 12 weeks before receipt of study intervention.
3. Female participants of childbearing potential or male participants who are able to father children and are willing to use acceptable methods of contraception for at least 28 days after the dose of study intervention; or female participants not of childbearing potential; or male participants not able to father children.

Note: Female participants of nonchildbearing potential must meet the criteria described in the WOCBP section of the protocol.

4. Capable of giving signed informed consent, which includes compliance with the requirements and restrictions listed in the ICD and in this protocol.

Exclusion Criteria

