Specialty sites: Obtain blood sample for immunogenicity assessment	~20 mL (for immunogenicity) [REDACTED]	~20 mL (for immunogenicity) [REDACTED]	
• Blood samples from participants enrolled at specialty sites (n=15/group).• [REDACTED]
Other sites: Obtain blood sample for immunogenicity assessment	~60 mL	~60 mL	
• Blood sample for Visit 1 will be collected prior to administration.
Administer study intervention	X		
• See Section 6.1 for additional information.
Observe and record acute reactions for 30 minutes after study intervention administration	X		
Provide a participant contact card	X		

PFIZER CONFIDENTIAL

Visit Identifier Visit Description	Visit 1	Visit 2	Notes
	Study Intervention Administration	Follow-Up After Study Intervention Administration	
Visit Window (Days)	Day 1	28 to 42 Days After IP Administration	
Provide participant with an e-diary (device or application), thermometer, and measuring device, and instruct to collect prompted local reactions and systemic events	X		
See Section 8.4.3 for follow-up AE and SAE assessments.Participants will record in an e-diary prompted local reactions and systemic events occurring within 7 days after administration. Instruct the participant to complete the e-diary from Day 1 through Day 7, with Day 1 being the day of study intervention administration. Participants will be instructed to contact the study staff or investigator if they experience redness or swelling measuring >20 measuring device units, severe pain at the injection site, or any Grade 4 prompted systemic event.
Review e-diary		X	
Designated site staff will review e-diary data online at frequent intervals (daily is optimal) for the 7 days following administration to evaluate participant compliance and reported events as part of the ongoing safety review.
Collect e-diary or assist the participant to delete the application		X	
Any e-diary devices given to participants are to be collected at Visit 2.
Record and report AEs and SAEs	X-----X		
AEs include nonserious AEs and SAEs.See Section 8.4 for additional information.

PFIZER CONFIDENTIAL

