8.2. Efficacy and/or Immunogenicity Assessments

Blood will be collected before study intervention administration (Visit 1) and approximately 1 month after administration (Visit 2) to assess immunogenicity.

Approximately 135 participants (approximately n=15/group) will be enrolled at specific investigator sites, [REDACTED]

[REDACTED] and approximately 20 mL of blood will be collected for sera measurements of immunogenicity (OPA titers and IgG concentrations) at each time point (Visit 1 and Visit 2). The remaining approximately 270 participants enrolled at other sites (approximately n=30/group) will have approximately 60 mL of blood collected for measurement of immunogenicity (OPA titers and IgG concentrations) at each time point (Visit 1 and Visit 2).

[REDACTED]

[REDACTED]

Immune Responses

OPA titers and IgG concentrations [REDACTED] will be measured in sera collected at Visits 1 and 2.

[REDACTED]

[REDACTED]

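### Section 8.10.1 gives one Visit 1 blood-draw instruction for all sites, while the synopsis, SoA and Section 8.2 split the draw by site type

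*Protocol*

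**What the plan says.** Three places in the protocol describe blood sampling by site type.

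- **Section 8.2.** For the specialty subset: "Approximately 135 participants (approximately n=15/group) will be enrolled at specific investigator sites". After a blacked-out stretch the text continues: "and approximately 20 mL of blood will be collected for sera measurements of immunogenicity (OPA titers and IgG concentrations) at each time point". The remaining 270 or so participants, about 30 per group, have about 60 mL drawn at each visit.
- **Section 1.1 (Synopsis).** About 15 participants per group are at specialty sites, which make a redacted collection and also draw about 20 mL for sera. For everyone else: "The remaining participants enrolled at other sites will have 60 mL of blood drawn for sera for OPA and IgG measurements".
- **Section 1.3 (SoA).** There are separate rows for specialty sites and other sites. The specialty row shows about 20 mL for immunogenicity followed by a redacted entry, at both visits; the other row shows about 60 mL. On timing: "Blood sample for Visit 1 will be collected prior to administration".

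Section 8.10.1, the step list for Day 1, has one line under the post-randomization steps: "Collect approximately 60 mL of blood prior to study intervention administration". It carries no site qualifier, names no second collection and has no cross-reference to the SoA or Section 8.2. The injection step directly below it does carry a cross-reference, to Section 6.1. No redaction mark is visible at the blood-draw line.

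The Visit 2 list in Section 8.10.2 contains a fully blacked-out bullet and no visible blood-draw bullet.

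**The concern.** A coordinator at a specialty site who works from the Day 1 step list sees one volume and no mention of the specialty collection. In the synopsis and Section 8.2, about 60 mL is the figure for other sites only.

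The draw must come before the injection, and SAP Section 3.4 counts only samples taken before dosing at Visit 1 as baseline. A missed or wrongly divided Visit 1 collection cannot be made good later. The data at stake are the baseline values for the redacted specialty-site assessment, planned in about 15 participants per group. A lesser possibility is that a participant gives a volume of blood that was not planned, if a site tries to satisfy both instructions.

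**Working it through.** **Inputs.** Nine groups of 45 (Protocol Section 4.1); about 15 per group at specialty sites and about 30 per group at other sites (Section 8.2); about 20 mL for sera at specialty sites and about 60 mL at other sites (Sections 1.1, 1.3 and 8.2); about 60 mL for all sites in Section 8.10.1. The volume of the specialty collection, V, is redacted.

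**Step 1: reproduce the plan's counts.**
- Specialty sites: 15 × 9 = 135, as stated.
- Other sites: 30 × 9 = 270, as stated.
- Total: 135 + 270 = 405 = 45 × 9, as stated.
- Share exposed to the ambiguity: 135 / 405 = 33.3%.

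**Step 2: does 60 mL conflict with the specialty total?** The specialty total is 20 + V. V is not visible, so the values below are an assumed range.

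| Assumed V (mL) | Specialty total, 20 + V (mL) | Total minus 60 (mL) |
|---|---|---|
| 20 | 40 | −20 |
| 40 | 60 | 0 |
| 60 | 80 | +20 |
| 80 | 100 | +40 |
| 100 | 120 | +60 |

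At V of about 40 mL the totals agree. At the other values they differ, in either direction. The documents do not show which case applies.

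**Step 3: is the step complete for any V?** No. Even at V = 40 mL, Section 8.10.1 does not say that about 20 mL goes to sera and the rest to another collection, nor that another collection exists.

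**Step 4: what could be lost?** Each specialty participant without a usable Visit 1 collection removes 1/15, about 7%, of a group's planned specialty baseline.

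**Step 5: are the main analyses touched?** The primary endpoints are reactogenicity, AEs and SAEs (Protocol Section 3). The secondary analysis is the group OPA GMT at 1 month with a t-based interval (SAP Section 6.2.1.1), which uses no baseline value. A specialty site that put all 60 mL into serum would still have more than the 20 mL or so planned for OPA and IgG. Neither analysis depends on how the Visit 1 line is read.

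**The case against.** The strongest reply is that sites already have clear instructions. The SoA has labelled rows by site type, Section 8.2 repeats the split for both visits, Section 8.1 makes adherence to the SoA essential, and the same section promises detailed collection instructions before the study starts. Specialty sites are also defined by the extra collection they make, so they are unlikely to overlook it. This argument stands as a reason for low severity. It does not remove the inconsistency, because the SoA introduction refers readers to the assessments and procedures section for the detail of each procedure, and Section 8.10.1 is part of that section. The SoA therefore does not plainly override it.

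Four stronger readings are tempting, and the documents do not support them.

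- **A threefold serum mismatch.** Setting 60 mL against 20 mL gives 60 / 20 = 3, or 40 mL too much. But the Section 8.10.1 line speaks of blood, not serum, so this compares what may be a total with one component of the specialty draw.
- **More blood than the SoA allows.** The specialty total in the SoA is redacted, so no excess can be computed.
- **About 135 baselines at risk of being lost.** This is the size of the subset that the ambiguous line applies to. The documents give no basis for an expected number of errors.
- **A missing split at Visit 2.** The relevant bullet may be the one blacked out, so nothing can be said about it beyond asking the sponsor to check.

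It is also fair to say that the sampling design itself is consistent, since three places agree on it. The fault is an omission in a step list.

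**Conclusion.** The point holds as an internal inconsistency of low severity. The Visit 1 step in Section 8.10.1 is, for the specialty sites, either wrong on volume or incomplete, and it is incomplete whatever the redacted volume is. It applies to about 135 of 405 participants (33%).

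The exposure is limited to the pre-dose baseline of the redacted specialty-site assessment and possibly unplanned blood volume in that subset. The primary safety analyses and the 1-month OPA GMT are unaffected, and no sample-size figure changes.

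This rests on two assumptions. The first is that the blacked-out text beside the 20 mL figure describes a further collection, which follows from the wording of the synopsis and the layout of the SoA although its type and volume cannot be seen. The second is that no site qualifier has been removed from the Section 8.10.1 line, which reads as a complete sentence. Which volume is correct is not judged here.

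**What to change.** Reconcile Section 8.10.1 with the synopsis, the SoA and Section 8.2. Either split the bullet by site type so that it mirrors the two SoA rows, naming the specialty collection and keeping the pre-dose timing, or replace the volume with a reference to those rows and Section 8.2. At the same time, confirm that the Visit 2 text in Section 8.10.2, partly redacted in the public version, carries the same split.

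The cost is one line in the protocol or a clarification letter to sites. It adds no procedure and leaves the analysis plan as it is.
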